Participants will receive a transportation refund for all study visits. This reimbursement will be determined based on the distance from the participant's home to the clinic, and can range from 10,000 UGX to 30,000 UGX. Additionally, participants will receive an incentive of 20000 Ush to compensate them for their time.

VIII. RISKS AND DISCOMFORTS: The potential risks incurred by participating in the studies include:

1. Risk of acquisition of HIV: Based on inclusion criteria, all participants will be at risk for acquiring HIV. It is therefore possible that some participants will become infected over the course of the follow-up study. All participants will be offered comprehensive counselling regarding HIV risks as well as safer conception risk. Participants will be counselled about and able to access condoms in the clinic. Women who seroconvert will be offered comprehensive HIV care at the ISS clinic.
2. Risk of developing resistant virus: Women who become acutely infected with HIV while incompletely taking TDF/FTC PrEP have an increased chance of developing resistant virus. Quarterly adherence counselling sessions will emphasize that women should come to the clinic for additional testing should she develop symptoms of acute HIV infection. Furthermore, if women adhere well, the risk of getting HIV and therefore of getting resistant virus is low.
3. Risk of partner related violence: We will promote serostatus disclosure between partners as part of our safer conception strategy. Discovery of HIV-serodiscordant status may be associated with harm to women. In addition, women who do not disclose PrEP use, may be at risk for partner-related violence should her use of this drug be discovered, given the implications that she therefore perceives herself to be at risk for HIV acquisition. In order to reduce the chance of partner violence we will facilitate referrals to couples-based HIV counselling and testing in the same space as the research is conducted.
4. Risk of Adverse effects related to taking TDF/FTC PrEP: TDF/FTC is first-line therapy in the treatment of HIV. In patients taking TDF/FTC with other HIV medicines to treat HIV infection, common side effects include: diarrhea, nausea, tiredness, headache, dizziness, depression, problems sleeping, abnormal dreams, and rash. In clinical trials of TDF/FTC as PrEP in which most people took study drug, side effects were reported by about 10% of participants (including those in the placebo group). In the Partners

PrEP study group the most common reported symptoms was headache reported by 16% in each group (TDF, TDF/FTC, and placebo.) Other risks reported with TDF/FTC exposure include: gastrointestinal intolerance, such as nausea, diarrhea or vomiting, and flatulence. Rare but serious side effects (not reported in PrEP trials to date) include lactic acidosis/ severe hepatomegaly with steatosis, renal impairment, including cases of acute renal failure and Fanconi's syndrome (renal tubular injury with severe hypophosphatemia), increase in bone metabolism leading to osteopenia, hypersensitivity reaction, acute exacerbation of hepatitis B infection, body fat redistribution, and risk of drug resistance in individuals with undiagnosed HIV. Women will be expressly counselled on the risks and benefits of PrEP during both the periconception and pregnancy period according to CDC and WHO guidelines. Women will be closely monitored in study visits and complete symptom logs. A clinician will be a part of the study staff and PrEP will be held or discontinued for women experiencing adverse effects based on his/her clinical judgment. Data on adverse events and side effects will be reported to the Antiretroviral in Pregnancy Registry.

5. Risk of Stigma: There is a potential that enrolled participants will be stigmatized if they reveal their involvement with the study or become associated with the study in some other way.
6. Social harms and psychological stress: Social harm, including emotional distress (e.g., stigma, compromise of reproductive autonomy), is a potential risk for participants. Another potential risk for participants is psychological harm, where the participant may possibly behave in a manner indicating distress (crying, showing aggression) or verbally expresses anxiety, fear or anger regarding own and or a partner's HIV serostatus or new STI diagnoses, interpersonal and or abuse issues within their partnership, pregnancy and or HIV serostatus disclosure concerns, as well as concerns with PrEP initiation and or adherence. Should this occur the protocol for managing participant distress will be implemented. The study team member will immediately stop the study procedures and talk with the participant about referral to a counsellor for support. Distressed participants will be referred to the local clinic for psychological counselling as per the routine standard of care at the clinic (please see Participant Distress Referral Form). After some time is allowed for recovery, the study team member will follow up with the participant to check their progress.
7. Risk to confidentiality: Risk to confidentiality exist in all studies. To protect against breach of confidentiality, participants will be assigned a unique study identifier, participant names will not be used in any recorded interviews or paper forms, all documents will be kept in locked cabinets in the study site office in the ISS clinic in Mbarara. All other study data will be associated with participants' coded identification number only. A master list of participant names and their code numbers will be stored in a locked file cabinet separate from the rest of the data. Only [name], [name] and the study coordinator will have access to the list, which will be destroyed within two years of publication of study findings, or if there is no publication, no later than six years after the study has ended. All interviews will be conducted in private locations at the research site. Safer conception counselling and adherence counselling will occur in individual sessions with a trained counsellor. All data will be kept confidential and stored in locked cabinets within restricted areas of MUST. All key drives and computers will be password protected. Sexual behaviour data collected by SMS will be protected in the servers and the messages themselves will be password protected.
8. Risk of time inconvenience: There may be a time inconvenience to study participants but the study staff will work with participants to reduce study visit burden while still maintaining the integrity of the research aims.

9. **Risk of discomfort:** There is a risk that participants may feel uncomfortable discussing issues related to HIV status, STI history, fertility desires and other emotionally-charged or personal subjects during visits. However, we do not wish for this to happen, and participants may choose not to answer if talking about these issues makes them uncomfortable. On-site counselling services will be made available for participants who express distress. In addition to psychological discomfort, participation in blood draws for testing may result in physical discomfort including but not limited to: faintness, inflammation of the vein, pain, bruising and/or bleeding at the puncture site. There is also a small possibility of infection. The physical discomfort from blood draw is unlikely to result in any serious adverse reaction but may cause irritation at the puncture site for several days. In order to best protect participants from potential discomforts phlebotomy procedures for biological and adherence testing will be performed by experienced personnel under sterile conditions. Vaginal swabs can also cause some discomfort both physically and potentially psychologically, but this will be minimized by encouraging all women to self-collect vaginal swabs.
10. **Unforeseen Risks:** The study medicine is investigational for use as PrEP (but approved for treatment of HIV) in Uganda. It is approved for use as PrEP in the U.S. and Europe and recommended by the W.H.O. However, there may be unforeseen or unknown risks or side effects. Women will be expressly counselled on the potential for unforeseen risks before initiating or continuing TDF/FTC as PrEP during periconception. In addition, women will be counselled on how and when to contact the study clinician if they experience any additional or potentially unforeseen side effects throughout their study participation. Given the data acquired to date in large clinical trials and demonstration projects of TDF/FTC as PrEP and the decades' experience using TDF/FTC for the treatment of HIV, there is no reason to expect that the drug will not work as intended.

IX. POTENTIAL BENEFITS

Potential benefits to participants: The participant may benefit from the information gathered from this study by learning strategies for reducing periconception HIV transmission. Participants who choose to initiate and adhere to safer conception strategies will also be engaging in HIV-risk reduction. PrEP and safer conception education are not routinely offered in the public health sector. Women participating in the study may have a reduced risk of HIV transmission by virtue of their participation. Evaluating uptake of and adherence to antiretrovirals as pre-exposure prophylaxis in this population is crucial to understanding whether and how this prevention strategy should be incorporated into HIV-risk reduction packages for at-risk women planning or with pregnancy. Women will also benefit from receiving objective STI testing to achieve an accurate diagnosis and treatment for their STIs which will result in decreased morbidity for the participant and her potential children. In addition, participants will have access to regular testing and referrals to ongoing care.

Potential benefits to society (e.g., increased understanding of disease processes): Women who choose to conceive with an infected or unknown serostatus partner in HIV-endemic settings need prevention strategies to reduce periconception HIV acquisition risk. Women at high risk for acquiring HIV during pregnancy also need risk reduction strategies to protect themselves and their babies. Evaluating uptake of and adherence to antiretrovirals as pre-exposure prophylaxis is crucial to understanding whether and how this prevention strategy should be incorporated into HIV risk reduction packages for at risk women planning or with pregnancy. Many PrEP studies focused on men who have sex with men (MSM) have shown that patients have an increase in

STIs.[69, 70] Understanding the STI risk among women, especially in the periconception period is a crucial first step in the process of designing PrEP programs and understanding patient risk in regards to HIV and STIs.

X. ALTERNATIVES TO PARTICIPATION

Participation is completely voluntary. Deciding not to participate will not have any bearing on the participant’s ability to access clinical existing clinical services.

XI. SOURCES OF ADDITIONAL INFORMATION

For the duration of the study, enrolled women will be under the care of [name] [name] who is the clinician for the study. Women will be expressly counselled on when and how to contact [name] [name] throughout the duration of their participation. [name] [name] and other study staff will be available to participants between their study visits to discuss potential symptoms or problems.

XII. MANAGEMENT OF ADVERSE EVENTS:

Adverse events and serious adverse events will be assessed and logged by study staff at each study visit. Unanticipated adverse events reported to the clinic staff or study clinician outside of normal study visits will be recorded and participants will be referred to appropriate care. All adverse events will be reviewed by the Principal Investigators and other relevant study/clinical staff and reported to appropriate study ethics committees (MUST IRB, Partners Healthcare IRB).

XIII. POST STUDY ACCESS TO TDF/FTC

PrEP is not currently provided in the public sector in Uganda. We will inform exiting participants about their options for accessing it in the private sector, or, should it become available, in the public sector.

XIV. BIOSTATISTICAL ANALYSIS

Analysis, Aim 1

Hypothesis: 70% of women will initiate PrEP as part of a safer conception strategy. In the Partners PrEP demonstration project, PrEP uptake is ~90% among uninfected women in mutually-disclosed serodiscordant partnerships ([name], personal communication). We expect uptake to be lower among women who are not in mutually-disclosed serodiscordant partnerships and who may worry about the effects of PrEP on pregnancy. We hypothesize that PrEP uptake will be associated with relationship power and social support.

Table 4. 95% CIs for range of uptake and adherence.		
% uptake or adherence	Uptake, N = 150 95% CI	Adherence ¹ , N = 105 95% CI
50	42.5-57.5%	40.4-59.6%
60	52.6-67.4%	50.6-69.4%
70	63.1-76.9%	61.2-78.8%
80	74.0-86.0%	72.3-87.7%
90	85.5-94.5%	84.3-95.7%
1. Detectable drug at visit 3 months after initiation		

Estimates of PrEP uptake: PrEP uptake/initiation is defined as the proportion of enrolled women who collect at least one 3-month supply of PrEP. A target sample size of 150 women produces a 95% CI width between 13% (when 70% initiate PrEP) and 15% (when 50% initiate PrEP) (Table 4.) We will calculate the prevalence (and 95% CI) of PrEP initiation using an intercept-only logistic regression model to account for potential clustering within the two groups (women enrolled through partners, women enrolled as individuals). We will describe, compare and test for differences between baseline characteristics of women who do and do not initiate PrEP. Log binomial regression with GEE will be used to estimate univariable and multivariable-adjusted risk ratios (RR) and 95% CIs for the associations between relationship power/social support and PrEP initiation. We will assess potential confounding factors individually; any factor with $P \geq 0.20$ will be excluded from further consideration and the remaining covariates entered into a multivariable model.

Analysis, Aim 2

Hypothesis: 70% of women will have detectable drug 3 months after PrEP initiation.

Estimates of periconception PrEP adherence:

Periconception PrEP adherence will be defined as PrEP initiators with plasma TFV concentration $\geq 40\text{ng/mL}$ three months after initiating PrEP. A target sample size of 105 women initiating PrEP will provide 95% CI width of 18% when

the percent of high adherers is 80% (Table 4). Secondary adherence outcomes are based on Wisepill device monitoring. We will determine the mean and median number of pills taken as well as patterns of adherence (gaps). We will consider Wisepill adherence as a binary outcome defined as taking $\geq 80\%$ of prescribed doses based on biologic plausibility and prior studies [23, 65, 71, 72]. Monthly assessments of median (interquartile range) adherence and number of 72-hour adherence gaps will be used to examine longitudinal trends in adherence.

We will calculate prevalence (and 95%CI) of PrEP adherence using an intercept-only logistic regression model with GEE. Log binomial regression with GEE will be used to estimate univariable and multivariable-adjusted risk ratios (RR) and 95% CIs for the associations between relationship power/social support and PrEP adherence.

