3. PrEP gives uninfected women a strategy to protect herself (and therefore her child) from HIV. Women who partner with an HIV-infected man have limited power to negotiate safer sex or safer conception practices [3, 10, 32]. HIV-uninfected women partnered with men living with HIV describe obligations to meet childbearing expectations, irrespective of HIV risk [10]. In oral PrEP trials with high adherence, women experienced a reduction in HIV acquisition of 63-75% [23, 24]. Among women with plasma concentrations of tenofovir indicating recent dosing, protection was estimated at 94% [25]. While women who enrolled in PrEP trials without being in mutually-disclosed serodiscordant partnerships had particular challenges taking study drug [33, 34], studies since PrEP efficacy has been proven suggest that this population is able and willing to take daily, oral PrEP [35]. Many of the barriers to adherence described by VOICE and Fem-PrEP trial participants with low adherence related to lack of proven efficacy of study drug, low risk perceptions, and wanting study services without taking study drug [36, 37]. The current proposal avoids these pitfalls by communicating unequivocal PrEP efficacy to women who believe their partner is HIV-infected and plan to conceive a child. Furthermore, PrEP acceptance is not a requirement of the study, which minimizes incentives for initiating PrEP without intent to use PrEP.

Given the limited prevention options for women who choose to conceive with HIV-positive men, WHO guidelines highlight serodiscordant couples considering conception are a priority group for PrEP[38]. The FDA labeling information and the U.S. Perinatal ART Guidelines support periconception PrEP use [16, 30, 39-42]. However, there are no data on feasibility and uptake of this strategy in settings with generalized epidemics.

II. RESEARCH DESIGN AND SPECIFIC AIMS

Table 2. Conceptual framework for pregnancy-related PrEP adherence

Domain	Construct	Measure(s)
Individual	HIV Knowledge	HIV knowledge [43]
		Safer conception knowledge[44]
	Risk	Partner serostatus
		Risk perception [45]
		Risk behavior via diary
	Optimism	PrEP optimism [46]
	Motivation	Parenthood motivation [47]
Medication side effects		
Socio-demographics	e.g. asset index, substance use, reproductive history, partnership type	
Couple	Partnership disclosure	HIV disclosure [48, 49]
		Complete couples-based HIV counseling and testing
	Communication, gender norms	Relationship power [50]

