Upon completing the informed consent process, interested participants will be asked to sign or fingerprint a copy of the written informed consent to confirm that they understand the study and what is expected of them as a research participant. A copy of the signed consent form will be given to the participant for their records. After signing of the consent, participants will be considered enrolled as part of the sample goal of 150 uninfected women.

Enrolled women will participate in the outlined mixed-method study to evaluate prevalence and determinants of uptake and adherence (tenofovir plasma concentration >40ng/mL, taking >80% of dispensed pills) to daily, oral TDF/FTC PrEP during periconception among HIV uninfected Ugandan women reporting HIV-infected or unknown serostatus partners. To accomplish this, women will participate in quarterly study visits, HIV and pregnancy testing, questionnaires and safer conception/adherence group counseling sessions. Participants will be eligible to initiate PrEP at any time during the first 6 months of the 9-month (maximum) study follow-up period. Participants will receive a PrEP referral form to bring to the clinic if they chose to initiate PrEP outside of a scheduled study follow up visit.

Women who become pregnant or test positive for HIV during the 9-month follow-up period will complete exit activities (questionnaire and in-depth interview) and be referred to appropriate antenatal and/or HIV follow-up care.

Counseling

Comprehensive safer conception counselling: Enrolled women will be offered a package of safer conception counselling for uninfected women who want to conceive a child with an infected partner:

- Encourage partner testing and serostatus disclosure within the partnership.
- Encourage partner to initiate ART if he is eligible by national guidelines (CD4 cell count \leq 500 or in serodiscordant partnership),
- Delay sex without condoms until he achieves HIV viral load suppression or is on ART x 6 months,
- Consider contraception to delay pregnancy until safer conception strategies implemented
- Limit sex without condoms to peak fertility, and / or
- Consider sperm washing, donor sperm, and adoption as alternatives.

Safer conception counselling will occur at baseline and then quarterly thereafter in non-pregnant women

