Adherence support counselling: Brief adherence counselling and support sessions will be available at to all women at the time of enrollment and will cover PrEP education. Follow-up adherence counselling will be available during quarterly visits to all women who initiate PrEP. Counselling will be performed by trained study counsellors in a individual counselling session. These sessions will discuss barriers to and promoters of adherence. **Data Collection (Table 3)**

Demographics: We will collect baseline demographic and reproductive health data (number of prior pregnancies, live births, living children) at enrollment. We will update demographic data at study exit to assess information that may change throughout the course of the study (e.g. employment, household income).

Measures: Constructs will be assessed with a questionnaire administered at 0 months and study exit (Table 2). *Other safer conception behaviors* will also be assessed, including partner HIV status, delay of sex without condoms until partner on ART with viral load suppression, accessing additional services such as sperm washing.

Sexual Behavior: Sexual behavior will be assessed through monthly diaries. The counsellor and the participant will fill in the first day of next anticipated menses on a monthly calendar and then participants will mark the number of condomless sex acts and bring this form back in for review at quarterly follow-up visits. We will use the sexual behavior data of woman who chose not to initiate PrEP to explore between group differences among individuals who chose to and who chose not to initiate PrEP. In addition, we will be able to better understand the entire sample's understanding and use of the alternative/additional safer conception strategy of timing sex to peak fertility by collecting this data regardless of PrEP initiation.

Biologic tests; All participants: All participants will complete quarterly urine pregnancy tests, rapid HIV tests and syndromic screening for STIs.

Beta hcg-urine pregnancy tests require approximately 4 drops of urine to test for human chorionic gonadotropin, a hormone that is produced once a woman becomes pregnant. Women who test positive for pregnancy after enrolment will be referred to appropriate antenatal care before being exited from the study.

Rapid HIV testing will occur via the standard of care finger-prick blood sample. HIV finger-prick testing will entail the clinical study member pricking the tip of the participant's

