STI Treatment: Participants with positive STI testing will receive treatment at the study site dispensed by a licensed medical professional who is a member of the study team. All treatment regimens will be in accordance with standard Ugandan treatment guidelines. Study participants with positive STIs who receive treatment will also be given treatment medications to deliver to their partner(s) with the goal of preventing reinfection. This practice of patient-delivered partner medication has been shown to be efficacious in several settings, including Uganda [61].

Biologic tests; Women who initiate PrEP: Women who initiate PrEP will complete creatinine at baseline and quarterly and hepatitis B safety monitoring at baseline to ensure that there are no contraindications to using PrEP. A nurse will also assess for any symptoms experienced after initiating PrEP to evaluate for any medication side effects. Blood testing for renal function (Creatinine) and for hepatitis B infection will require 2 tubes of blood or approximately 10mL or <1 tablespoon of blood at baseline and 1 tube of blood or approximately 5mL quarterly. As per WHO guidelines, women will be eligible to initiate PrEP immediately. Women with abnormal renal function or active hepatitis B infection (HBV surface antigen positive) will be instructed to stop PrEP. Abnormal renal function will be defined as:

- Non pregnant women: serum Creatinine > 89 µmol/L and GFR < 60ml/min (Glomerular filtration will be estimated using the Cockcroft-Gault equation).

Any woman who has abnormal safety lab results will be referred to appropriate clinical care.

Adherence: Adherence of PrEP will be assessed by biological sampling as well as electronic data capture monitoring. In addition to assessing adherence we will promote adherence through offering individual adherence counselling sessions to all women who initiate PrEP at their study visits using an adherence counselling tool developed specifically for PrEP adherence.

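### Aim 1 scores PrEP uptake as ever/never over a 6-month offer that pregnancy exit can cut short, so the risk ratio for relationship power or social support can mix the decision to start with the time available to start

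*Combined protocol and SAP*

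**What the plan says.** - **Offer.** Section V, Overview: "Participants will be eligible to initiate PrEP at any time during the first 6 months of the 9-month (maximum) study follow-up period". A woman may start at once ("As per WHO guidelines, women will be eligible to initiate PrEP immediately", section V, Biologic tests for women who initiate PrEP). She may also start between visits: "Participants will receive a PrEP referral form to bring to the clinic if they chose to initiate PrEP outside of a scheduled study" follow-up visit. Table 3 has a separate initiation visit.
- **Exit.** Section V, Overview: "Women who become pregnant or test positive for HIV during the 9-month follow-up period will complete exit activities". The text on biologic tests for all participants repeats this: "Women who test positive for pregnancy after enrolment will be referred to appropriate antenatal care before being exited from the study". Testing is at scheduled visits: "All participants will complete quarterly urine pregnancy tests, rapid HIV tests and syndromic screening for STIs".
- **Outcome.** Section XIV, Analysis, Aim 1: "PrEP uptake/initiation is defined as the proportion of enrolled women who collect at least one 3-month supply of PrEP".
- **Association.** The same section relates this binary outcome to relationship power and social support by log binomial regression with GEE. It has no term for time under offer, no early uptake window, and no rule for women who leave before month 6 without having started.
- **Power and conception.** Section I, Significance, item 3: "Women who partner with an HIV-infected man have limited power to negotiate safer sex or safer conception practices". This describes women with HIV-infected partners as a group. It does not compare conception timing by level of relationship power.

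**The concern.** Eligibility requires that the woman or her partner wants a child within a year, so pregnancies in the first months are expected. Take two women who have not collected PrEP by month 3. One is found pregnant then and exits. The other stays to month 6 and still does not start. Both are scored as non-initiators, but the first had only about half the offer.

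This matters for the association more than for the description. If relationship power or social support is related to how soon women conceive, it is also related to how long they are under offer. The RR can then move away from 1 although the exposure has no bearing on the decision to start, or a true association can be hidden. The confounder screen does not help, because conception happens after baseline. The baseline comparison of initiators with non-initiators contains the same mixture.

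**Working it through.** **The plan's yardstick.** Table 5 gives a minimum detectable RR of 1.27 for N = 150, 40% with high relationship power and 70% uptake in the unexposed. Check with 90 women at 0.70 and 60 at 0.70 × 1.27 = 0.889:
- Pooled proportion 0.776, null SE 0.0695, alternative SE 0.0631.
- z = (0.189 − 1.96 × 0.0695)/0.0631 = 0.84, so power is 79.8%.

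The cell reproduces at a two-sided alpha of 0.05. The table title prints 0.5, which reads as a misprint.

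**Inputs.** From the documents: 150 women, 70% uptake (here, uptake if nobody exited), a 6-month offer and quarterly testing. The 40% with high power is one of Table 5's scenarios. Assumed, because the documents give no figure: 50% or 30% of all women start at enrolment, and monthly conception rates (low vs high power) are 8 vs 4%, 12 vs 6% or 15 vs 5%. Power has no effect on the decision to start, so the true RR is 1.00.

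**Formulas.** Let s be the share starting at enrolment, with later starts at a constant rate that brings uptake to 70% by month 6. Then r = √(0.30/(1 − s)) is the fraction of not-yet-started women who remain so over a quarter.
- Starts in months 0-3: a = (1 − s)(1 − r). Starts in months 3-6: b = (1 − s)r(1 − r).
- s = 0.50: r = 0.775, a = 0.113, b = 0.087. s = 0.30: r = 0.655, a = 0.242, b = 0.158.
- Conceived by month t at monthly rate λ: c(t) = 1 − exp(−λt).

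Observed uptake P:
1. Starts at any time, exit at the next quarterly visit: P = 0.70 − b·c(3). Only pregnancies found at month 3 cost starts.
2. Women stop starting at conception itself: P = s + (1 − s)·k/(k + λ)·[1 − exp(−6(k + λ))], with k = −ln(r)/3 (0.085 or 0.141).
3. Starts only at months 0, 3 and 6: P = s + a[1 − c(3)] + b[1 − c(6)].

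Example for (1), s = 0.30 and 15 vs 5%: c(3) = 0.362 vs 0.139. Low power 0.70 − 0.158 × 0.362 = 0.643; high power 0.70 − 0.158 × 0.139 = 0.678; RR = 1.05.

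**Results.** Spurious RR, with the false-positive rate in brackets (pooled two-sample z test enumerated exactly for 90 vs 60 women, nominal 5%):

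| Start at enrolment | Conception per month, low vs high | (1) Any time, quarterly exit | (2) Stop at conception | (3) Visits only |
|---|---|---|---|---|
| 50% | 8 vs 4% | 1.01 (5%) | 1.03 (6%) | 1.04 (6%) |
| 50% | 12 vs 6% | 1.02 (5%) | 1.04 (6%) | 1.05 (7%) |
| 50% | 15 vs 5% | 1.03 (6%) | 1.06 (8%) | 1.09 (10%) |
| 30% | 8 vs 4% | 1.02 (5%) | 1.05 (7%) | 1.09 (10%) |
| 30% | 12 vs 6% | 1.03 (6%) | 1.07 (9%) | 1.12 (13%) |
| 30% | 15 vs 5% | 1.05 (7%) | 1.12 (15%) | 1.21 (25%) |

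If late starts are instead spread evenly over the 6 months, the last row of (1) becomes (0.70 − 0.20 × 0.139)/(0.70 − 0.20 × 0.362) = 1.07.

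**Bound for (1).** RR = (1 − g·cH)/(1 − g·cL), where g is the share of eventual initiators who would start after month 3, and cL and cH are conception by month 3 in low- and high-power women. The runs above have g = 0.087/0.70 = 0.125 and 0.158/0.70 = 0.226. At g = 0.5 with 40 vs 20% conceiving, RR = 0.90/0.80 = 1.13. At an extreme 50 vs 10%, RR = 0.95/0.75 = 1.27. As g approaches 0 (nearly all start at enrolment), RR approaches 1. Exchanging cL and cH inverts the RR.

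**The case against.** Four points can be made for the plan.

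1. **The offer is flexible.** PrEP can start at enrolment and between visits by referral form, so a woman exited at month 3 still had about three months of offer. This stands. Column (3) treats starts as tied to visits and is an upper case; column (1) is closest to the text.
2. **The direction is not in the documents.** A reader might infer that women with low relationship power conceive sooner, so that the hypothesised positive association would appear as an artefact. The documents do not support that. They say only that women with HIV-infected partners have limited negotiating power. A woman with more control who wants a child could conceive sooner, and the bias would then reverse.
3. **Not every woman who conceives is affected.** One who has already collected PrEP remains an initiator. This stands.
4. **Ever/never uptake is a legitimate target.** Aim 1 asks what is associated with uptake as part of safer conception, and a woman who conceives before starting did not take it up. If an exposure lowers uptake through earlier conception, that is part of its total association. This stands, and it is a reason to keep the planned RR. It does not license reading that RR as evidence about the decision to start.

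The structural point survives all four: unequal time under offer enters the RR, and the plan has no analysis that would show it.

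**Conclusion.** The concern holds as a modest, conditional one. It requires that time to conception differ by relationship power or social support, and that a fair share of women start after enrolment. Neither is known from the documents.

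Under the stated assumptions the spurious RR is about 1.01-1.05 (5-7% false positives) on the reading closest to the text, or 1.07 at most if late starts are spread evenly. It is about 1.03-1.12 (up to about 15%) if women stop starting once they conceive. It reaches about 1.04-1.21 (up to about 25%) only if starts are in practice confined to visits. Against a minimum detectable RR of 1.27, the first range is small, while the upper ends of the others are a material share of the effect sought.

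The documents do not support concluding that a positive Aim 1 result would be an artefact, or that the ever/never outcome must be replaced.

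**What to change.** Keep the ever/never proportion and the log binomial RR as planned. Add to section XIV, Analysis, Aim 1:

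- **A supporting time-to-event analysis.** Model time from enrolment to first PrEP collection over 6 months, with pregnancy or HIV exit as a competing event that ends time at risk. Report cause-specific estimates for relationship power and for social support. Where women can start until they exit, as in column (1), the cause-specific hazard ratio is 1.00 under no true association, by construction.
- **A sensitivity analysis** that ends time at risk at estimated conception where a date is available, because exit dates alone do not remove the bias in column (2).
- **A count** of non-initiators who exited before month 6, by relationship power level. If few, the issue can be set aside.
- **A reading rule.** If the two analyses disagree, do not attribute an ever/never association to the PrEP decision.

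The cost is SAP wording and a second estimate to report. The visits should already generate the collection and exit dates. Table 5's detectable RRs do not apply to the added estimate, so present it as supporting and without a power claim.
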